10.3 Measurement

There are six scheduled study visits during which clinical assessment and measurements will be made in this study:

Activity	Schedule
Visit 0	Screening
Visit 1	Randomization (Day 3-10 post antibiotics)
Visit 2	Week 3
Visit 3	Week 6
Visit 4	Week 10
Visit 5	Week 14
Visit 6	Week 18

Safety will be assessed at each visit using self-reported adverse events, symptoms and pelvic examination findings. Pelvic examinations at each visit will be used to evaluate subjects for signs of irritation involving the external genitalia, cervix or vagina.

The presence of a Symptomatic UTI episode will be assessed at each visit by the investigator using the case definitions in Section 3.3. Subjects will also be queried at each study visit regarding any Probable UTI episodes, which may have occurred since the prior visit. The number of days from the date of the Randomization Visit to the date when a recurrence of UTI is first diagnosed will be used to calculate the time to UTI recurrence. A new on-study UTI (Symptomatic or Probable UTI) can only be diagnosed after the urine culture at Visit 1, or at another interim study visit after confirming resolution of the prior UTI.

Vaginal microbiota will be assessed using the Nugent Scoring System for Gram Stained Vaginal Smears at Visits 1 through 6. Vaginal cultures of total lactobacilli and *E. coli* will be evaluated at Visits 1 through 6. Colonization with the exogenous *Lactobacillus crispatus* strain CTV-05 will be evaluated by the presence or absence of CTV-05 by rep-PCR at Visits 1 through 6. Vaginal fluid specimens from each visit will be stored for assessment of shifts in the composition of vaginal microbiota using qualitative and/or quantitative DNA amplification methods. Presence and/or quantity of H₂O₂, lactic acid, and cytokines will be assessed.

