4.4.2 Safety

Safety will be evaluated using the following safety measures:

1. Subjects will be queried about adverse events at all visits.
2. Subjects will be given a Study Diary to record symptoms.
3. Genital examinations at all visits. Complete pelvic exams at visit one and six or if clinically indicated.

4.4.3 *Lactobacillus* Colonization

Vaginal colonization with lactobacilli will be assessed by vaginal culture. This culture information will be both specific to *L. crispatus* CTV-05 and non-specific (total vaginal lactobacilli, including endogenous and exogenous lactobacilli).

Total *Lactobacillus* colonization and H₂O₂ production will be assessed using culture. Colonization specifically with *L. crispatus* CTV-05 will be assessed using a DNA fingerprinting technique known as rep-PCR (11), a repetitive element sequence-based PCR, which will be used to identify the specific strain of *L. crispatus* (CTV-05) by

amplifying its unique pattern of DNA fragments. This technique, which makes use of repetitive sequences dispersed throughout a bacterial genome for the direct amplification of genomic DNA, generates bacterial species- or strain-specific fingerprint patterns. Rep-PCR can be used to distinguish probiotic *L. crispatus* strain CTV-05 from other *L. crispatus* species. The *Lactobacillus* cultures and CTV-05 rep-PCR will be performed in the lab of [name]. at the University of Washington. The rep-PCR data collected will be used to assess the correlation between colonization and clinical endpoints.

Vaginal fluid specimens will be stored from each visit for analysis of shifts in the composition of vaginal microbiota by qualitative and/or quantitative DNA amplification methods. DNA amplification will be performed in the lab of [name] M.D. at the University of Washington.

4.4.4 *E. coli* Colonization

Vaginal colonization with *E. coli* will be assessed by vaginal culture at all visits. The *E. coli* cultures will be performed in the lab of [name]. at the University of Washington.

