At Visit 1, each subject who continues to meet all inclusion and exclusion criteria will be randomized and will receive a box containing 15 applicators. Two extra applicators will be kept at the study site in case a lost or damaged applicator needs to be replaced. The first study applicator will be inserted under supervision in clinic at this visit. The remaining 14 applicators will be inserted daily at bedtime on Days 2–5, and then weekly. Women are to abstain from sexual intercourse and tampon use for 24 hours after each applicator is used. If the subject's partner uses condoms, they will be instructed to use non-spermicidal condoms to avoid killing the *L. crispatus*. The use of other intravaginal products including douching is prohibited throughout the four-month study period. Subjects must agree not to self-medicate with antibiotics or antifungals during the four-month study period. However, subjects may be treated for any on-study vaginal or other infection if a health care provider deems such treatment necessary. Subjects who receive antibiotic or antifungal treatment after commencing the study should continue to insert the study applicator according to their allocated schedule.

Subjects will be provided with a Study Diary to use to record applicator use information during the study. The Study Diary will also be used by subjects to record any symptoms. Subjects will be instructed on how to use these memory aids to remind them to insert the applicator on the designated day and to record the date and time when each applicator was inserted.

Self-reported symptoms will be evaluated at all study visits. Subjects will be queried about the following symptoms:

Nausea or vomiting
Abdominal Discomfort
Diarrhea
Constipation
Rash
Abnormal Vaginal Discharge/Bleeding
Abnormal Vaginal Odor
Genital itching or burning
External genital irritation/swelling
Painful Urination
Urinary Frequency
Urinary Urgency
Blood in urine

Headache
Other: _____

Other: _____

Subjects will be instructed to call the study clinic if they have any unexpected symptoms at any time during the study.

Pelvic examinations will be performed at all visits to evaluate the external genitalia; cervix and vaginal mucosa for signs of irritation at Visits 1 and 6 and if clinically indicated.

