It is possible that the entry UTI episode will not be fully resolved at the time of randomization (Visit 1), as mild symptoms may still be present, and the dipstick and urinalysis may still be slightly positive or equivocal several days after completing antibiotics.

The following procedures and assessments will be performed at Visit 1:

1. Eligibility confirmed.
2. All baseline symptoms to be recorded on the CRF.
3. Urine pregnancy test performed in clinic.
4. Clean catch urinalysis and culture.
5. Vital signs.
6. Pelvic examination, to be conducted in the following order:
 - a. Examination of the external genitalia
 - b. Speculum insertion and examination of vagina, fornices and cervix with naked eye. Only water must be used to lubricate the speculum at all study visits. Other lubricants could kill *L. crispatus*.
 - c. Vaginal swab for pH, wet mount (clue cells), KOH and amine test (whiff test) performed in clinic.
 - d. Vaginal swab for gram stain Nugent score.
 - e. Vaginal swabs for culture (total lactobacilli and *E. coli*) and rep-PCR.
 - f. Swab of vaginal fluid to be stored for assessment of vaginal microbiota by DNA amplification.
 - g. Bimanual examination
7. Subject randomized.
8. First investigational applicator inserted under supervision.
9. Instructions provided to subject regarding:

- a. Study Diary
- b. Dates for initial 5 day applicator use and weekly applicator use will be marked on the Study Calendar, and staff will review with the subject how to record. If subject experiences unanticipated menses she may defer scheduled applicator use and will then record the day of actual use.

6.3.5 Visits 2 thru 5

The following procedures and assessments will be performed at follow-up Visits 2 thru 5 (unless otherwise specified):

1. All reported AEs to be recorded on the AE CRF.
2. Clean catch urine dipstick performed in clinic.
3. Urinalysis and urine culture.
4. Urine pregnancy test performed in clinic only if clinically indicated.
5. Focused physical examination, if indicated for assessment of symptoms and adverse events.
6. Pelvic examination to be conducted in the following order:
 - a. Examination of the external genitalia.
 - b. Vaginal swab for pH, wet mount (clue cells), KOH and amine test (whiff test) performed in clinic.
 - c. Vaginal swabs for culture (total lactobacilli and *E. coli*) and rep-PCR sent to laboratory
 - d. Vaginal swab for gram stain Nugent score sent to laboratory (Visit 5 only).

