10.10.2 Vaginal Colonization with Lactobacilli

Total lactobacilli (based on culture) will be scored as 1+, 2+, 3+, or 4+.

Colonization with *L. crispatus* strain CTV-05 (based on rep-PCR) will be scored as present or absent (frequency). Number and percent of subjects with positive CTV-05 in each treatment group will be presented. 95% confidence intervals will be calculated to evaluate any difference between the treatment groups.

The differences of these scores between Visit 1 (Day 1, Baseline) and Visits 3 and 6 for each subject will be evaluated within each group and between treatment groups.

10.10.3 *E. coli* Vaginal Colonization

The number (%) subjects with *E. coli* colonization in each treatment group will be summarized by treatment group and visit. 95% confidence intervals will be calculated to evaluate any difference between the treatment groups at a given visit.

10.10.4 Change in Vaginal Microbiota, as assessed by DNA amplification.

The number (%) of specific *Lactobacillus spp.* and uropathogens will be summarized by treatment group and visit. 95% confidence intervals will be calculated to evaluate any difference between the treatment groups at a given visit.

10.10.5 Safety and Tolerability.

The safety endpoints include specific solicited adverse events (AEs), all other reported AEs, serious adverse events (SAEs) and signs of irritation on pelvic examination. The adverse events emerging during the study, their severity and relation to study product will be recorded. Each event will be coded with system organ class and preferred term based on the Medical Dictionary for Regulatory Activities (MedDRA). Number (%) of subjects with AEs will be summarized by system organ class, preferred terms, and treatment group. Severity of AEs and relationship to study product will also be summarized by system organ class, preferred terms, and treatment group. SAEs and reasons for premature termination from study will be summarized by treatment group in frequency and percent. In addition, signs of irritation of the external genitalia, vagina or cervix from pelvic examination, along with their severity and relation to study product will be summarized by treatment group. Furthermore, symptoms and physical findings will be summarized.

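### Section 10.3 says the cervix and vagina are checked for irritation at each visit, but routine internal examinations fall only before the first dose and about 6–10 weeks after the last

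*Combined protocol and SAP*

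**What the plan says.** The statistical section and the procedural sections describe different examinations.

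- **10.3 Measurement:** "Pelvic examinations at each visit will be used to evaluate subjects for signs of irritation involving the external genitalia, cervix or vagina".
- **10.2 item 6** makes abnormal pelvic examination results over the four-month period part of the safety and tolerability endpoint.
- **10.10.5** summarises by treatment group "signs of irritation of the external genitalia, vagina or cervix from pelvic examination".
- **4.4.2 Safety:** "Genital examinations at all visits. Complete pelvic exams at visit one and six or if clinically indicated".
- **5.1** gives the external genitalia at all visits, but "cervix and vaginal mucosa for signs of irritation at Visits 1 and 6 and if clinically indicated".
- **6.3.5** opens with "The following procedures and assessments will be performed at follow-up Visits 2 thru 5". Its pelvic examination item then lists the external genitalia and swabs, with no speculum step.
- **6.3.4 (Visit 1)** does have that step: "Speculum insertion and examination of vagina, fornices and cervix with naked eye". It is item 6b. Randomization is item 7, and item 8 is "First investigational applicator inserted under supervision".
- **The flow chart** marks pelvic examination at Visits 1 and 6 only.

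Section 6.3 contains no procedure list for Visit 6, so the internal examination at that visit rests on 4.4.2, 5.1 and the flow chart.

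**The concern.** LACTIN-V is a topical vaginal product, so local irritation is a natural safety question and the period of interest is the dosing period. On the schedule as written, one routine internal examination is a pre-dose baseline and the other comes weeks after the product has stopped. Signs that appeared during dosing and then resolved would not be seen at Visit 6.

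Internal findings during dosing would come only from examinations prompted by symptoms or clinical judgement, or from women who leave the study early. Those women are selected, and the selection may differ by arm. Section 2.2.2.2 reports that in LV-003, which used the earlier capsule, vaginal discharge and odour were at least 5% more frequent on LACTIN-V than on placebo. If that pattern recurred, speculum examinations would be triggered more often on active product. Section 10.10.5 does not separate scheduled from triggered examinations and states no denominator for either.

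At stake is what the tolerability summary can support. A table built on 10.3's description would appear to cover vaginal and cervical signs over four months when the routine data cover only a baseline and an off-product time point.

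**Working it through.** **Inputs**

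- Daily doses on Days 1–5, then weekly from Day 8 (4.2).
- Weekly doses: 10 (4.1, 4.2, 10.1, flow chart) or 8 (3.4.1, 5.1). For the 8-dose version, the Day 8 start is carried over from 4.2 as an assumption.
- Last visit: Week 18 (10.3, flow chart) or Week 16 (4.3).
- Weeks are counted from Visit 1 and Week w is taken as Day 7w (assumption).

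**Reproducing the plan's own figure.** Section 4.2 states 15 applicators over 11 weeks. Total = 5 + 10 = 15. Last weekly dose = 8 + 7 × 9 = Day 71, which lies in week 11 (Days 71–77). The figure reproduces. The 8-dose version gives 5 + 8 = 13, the count in 6.7.

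**Gap from last dose to last visit** = 7w − last dose day.

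| Weekly doses | Last dose | Week 16 (Day 112) | Week 18 (Day 126) |
|---|---|---|---|
| 10 | 8 + 7 × 9 = Day 71 | 112 − 71 = 41 days (5.9 weeks) | 126 − 71 = 55 days (7.9 weeks) |
| 8 | 8 + 7 × 7 = Day 57 | 112 − 57 = 55 days (7.9 weeks) | 126 − 57 = 69 days (9.9 weeks) |

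The range is 41 to 69 days, about 6–10 weeks. The 10 further weeks off product described in 4.1 agree with the upper end.

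**Sensitivity to the counting origin.** Suppose Week 18 is counted from Visit 0, taken as 6 to 15 days before Visit 1 (3–5 days of antibiotic plus 3–10 days). The gap then runs from 126 − 15 − 71 = 40 days (5.7 weeks) to 126 − 6 − 57 = 63 days (9.0 weeks). Applying the same offset to Week 16 gives at the shortest 112 − 15 − 71 = 26 days. The last visit still falls after dosing.

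**Routine internal examinations during dosing**

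- Calendar of Weeks 3, 6, 10, 14 and 18: visits inside dosing are Weeks 3, 6 and 10 with 10 weekly doses (Day 70 is before Day 71), or Weeks 3 and 6 with 8.
- Calendar of Weeks 2, 4, 8, 12 and 16: visits inside dosing are Weeks 2, 4 and 8 under either regimen (Day 56 is before Day 57).
- All of these fall among Visits 2–5, whose list in 6.3.5 has no speculum step.
- Count: 0 under every combination.

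**The case against.** The strongest reply has three parts.

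**On-treatment data exist.** The external genitalia are examined at every visit. Symptoms are asked about at every visit, including genital itching or burning and external irritation or swelling (5.1). The diary grades symptom severity over the first 7 days, which covers daily dosing (Appendix B). All adverse events are recorded and summarised by arm. Section 6.3.6 calls for a pelvic examination, with a speculum step, for vaginitis symptoms, although that list is only a guide. Section 6.5 requires end-of-study procedures when a woman leaves the study before Visit 6, and the flow chart places a pelvic examination there. A reader might infer that the trial cannot show product irritation at all, or that exposure is never examined. These provisions rule out both inferences. They do not supply a systematic internal examination: 6.3.6 depends on symptoms, and 6.5 applies to leaving the study, while women who only stop product continue in follow-up (6.2.1.4).

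**Section 10.3 may be loose wording.** Four places agree on limited internal examination, and 5.1 and 6.3.5 both use the term pelvic examination for an external one. That is a fair account of how the conflict arose. But 10.3 names the cervix and vagina, and it sits in the section that defines what is measured for analysis.

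**Earlier studies looked internally.** Section 11.1.1 reports no significant differences in LV-001, which included colposcopy. Section 2.2.2.2 reports unremarkable colposcopy in LV-005 and no deep epithelial disruption in LV-006. These bear on whether more examination is needed, and limiting it may well have been deliberate. They cover shorter use: five doses in LV-001 and LV-005 (12 women in the latter), and five daily doses plus two weeks of weekly use in LV-006 (24 women). They do not make 10.3 true of this trial.

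A reader might also expect clean Visit 6 findings to be reported as no irritation over four months. Section 10.10.5 makes no such claim and does not restrict its summary to Visit 6. The risk lies in the absence of any rule against that reading.

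**Conclusion.** The contradiction stands. Section 10.3 claims assessment of the cervix and vagina at each visit, and the schedule provides it routinely only at Visit 1, before the first applicator, and at Visit 6, off product. The number of routine internal examinations during dosing is zero under either regimen and either visit calendar, so this conclusion does not depend on how those conflicts are settled.

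The gap of about 6–10 weeks does depend on them. It assumes weekly dosing from Day 8, weeks counted from Visit 1 and doses taken on schedule. Deferral for menses (6.3.4, 6.4.2) or late use of a missed applicator (6.6) could move the last dose later and shorten it.

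The consequence is limited but real. External and symptomatic irritation can be compared between arms on treatment. The between-arm rate of vaginal or cervical signs during dosing, particularly signs without symptoms, cannot be estimated systematically, and Visit 6 results cannot stand in for it.

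**What to change.** Reconcile 10.3 with 4.4.2, 5.1, 6.3.5, 6.5 and the flow chart, and state what the Visit 6 examination comprises, since 6.3 has no list for that visit. Which route to take is the sponsor's choice.

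**If the schedule is kept:**

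- Correct 10.3, and restrict 10.2 item 6 and 10.10.5 to: external genitalia at each visit; vagina and cervix routinely at Visit 1 (baseline) and Visit 6 (off product).
- In 10.10.5, report scheduled internal examinations separately from symptom-triggered and early-discontinuation ones, each with its own denominator (women examined, by arm).
- State that no conclusion about vaginal or cervical signs during dosing will be drawn from Visit 6.

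The cost is wording and one additional breakdown in the safety tables.

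**If 10.3 is meant to be met:** align the visit lists and the flow chart with it, so that scheduled internal examination falls within the dosing period. This costs a protocol amendment. Added examinations would burden participants, and relocating the Visit 6 examination would give up the routine late one.

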10.4 Statistical Power and Sample Size Justification

Based on previous studies in this population, we estimate that 40% of women with a history of rUTI and recent treatment for a UTI will have a recurrence within the 4 month follow-up period, based on data from a recently completed rUTI study at this site (17). We plan to enroll 250 women to allow for >80% power to detect a 50% reduction in UTI incidence, also factoring in some drop-out, non-compliance and loss-to-followup, plus a cushion in case of a recurrence rate of less than 40%.

10.5 Study Instruments

Responses to safety questions, results of clinical examinations, and results of laboratory testing will be recorded on source documents for visits and laboratory evaluations.

The study will continue enrolling subjects until all subjects are enrolled and have completed Visit 6, or until there is any finding that warrants change in study procedures, as explained previously (see Section 7.2 and 7.4).

10.6 Randomization

Subjects will be randomized in a double-blind fashion. The randomization assignments will be produced using a computerized blocked randomization process, assigning equal numbers of subjects to either intervention or placebo. The randomization assignments, along with the sequentially assigned identifying number (ID#), will be given to the Hall Health pharmacy, where the probiotic/placebo will be packaged into identical envelopes

marked with the ID# prior to distribution to clinic personnel. Subjects who have successfully completed the Screening Visit and the Visit 2 pre-randomization assessments will be randomized sequentially as they become eligible for the study.

10.7 Cohorts for Analyses

The intent-to-treat (ITT) cohort is defined as subjects who are randomized in the study.

The modified intent-to-treat (MITT) cohort is defined as subjects who are randomized and have received at least one dose of study product. It is a subset of the ITT cohort. It will be used for analyses of primary and secondary endpoints, baseline characteristics, trial conduct, and significant protocol deviations.

The evaluable (Eval) cohort is defined as the subset of the MITT cohort who had at least one follow-up visit assessment post-baseline (Visit 2 or later) and are not an antibiotic treatment failure at Visit 1 (defined as a requiring treatment for UTI symptoms at Visit 1). Subjects with any significant protocol deviations may be included in this cohort.

The according-to-protocol (ATP) cohort is the subset of Eval with subjects who meet all protocol specifications. Those subjects who developed exclusion criteria while on study will be excluded from this cohort.

Both Eval and ATP cohorts will be used to analyze the primary endpoints.

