In this Phase IIa study, twenty-four women with BV were randomized in a 3:1 ratio of active product to placebo. Participants used LACTIN-V at 2×10^9 colony-forming units (cfu)/dose or placebo for 5 initial consecutive days, followed by a weekly application over 2 weeks. They returned for follow-up on Days 10 and 28. Sixty-one percent of the 18 women randomized to the LACTIN-V group were colonized with *L. crispatus* CTV-05 at Day 10 or Day 28. Among LACTIN-V users with complete adherence to the study regimen, 78% were colonized at Day 10 or Day 28. Of the 120 adverse events (AEs) that occurred, 108 (90%) and 12 (10%) were of mild and moderate severity, respectively. AEs were evenly distributed between the LACTIN-V and placebo group. Of the total AEs, 93 (78%) were genitourinary in origin. The most common genitourinary AEs included vaginal discharge (46%), abdominal pain (46%), dysuria (21%), pollakiuria (21%), vaginal odor (21%), and genital pruritus (17%). No grade 3 or 4 AEs or serious AEs occurred and no deep epithelial disruption was seen during colposcopic evaluation. The product was well tolerated and accepted. The applicator and dosage modifications resulted in a more potent LACTIN-V product (Formulation 1 in applicator) and an improved clinical protocol, leading to higher colonization and thus greater efficacy to prevent recurrent BV (15).

In early clinical studies conducted by The Medicines Company between 1991 and 2000, a total of 304 women received Lactin-Vaginal and were considered evaluable.

Although the overall results of the phase II/III study with Lactin-Vaginal indicated no significant improvement in the cure rate for BV when the study product was administered with a single 2 gram dose of metronidazole, the subset of subjects colonized with *L. crispatus* CTV-05 had a better clinical outcome. In this study, Lactin-Vaginal was demonstrated to be safe, with no category of adverse events occurring at a statistically higher frequency in the Lactin-Vaginal group than among controls. Later studies conducted by Osel, Inc. with the product LACTIN-V (Formulation 1 in capsule) at 5×10^6 or 5×10^8 cfu/capsule (Protocol No. LV-001 through LV-004) included more than 200 women (half of them being exposed to LACTIN-V) and provided excellent data on the safety of the study product.

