6.6 Missed Applicators

During the initial five-day treatment period, if it is already within eight hours of her next dose, she should skip the missed applicator. The subject should record the missed dose on the Study Diary. After Day 5, if a subject misses an applicator, she should be instructed to use the missed applicator as soon as possible (but no more than four days from the scheduled date) and the date should be recorded on the Study Diary.

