8.6 Protocol Deviations

All significant protocol deviations that the Investigator or site staff believes are of major importance (for example, incorrect randomizations, subject enrolled but not eligible) should be reported to [name]. as soon as possible. Significant protocol deviations may include the following:

- Deviations from the Inclusion/Exclusion criteria that may affect subject safety.
- Deviations (omission or delay) of safety monitoring procedures.
- Deviations in the administration of study product.
- Deviations in obtaining informed consent.

Significant protocol deviations will be reported to the University of Washington IRB, and will also be recorded on the CRF using the Significant Protocol Deviation page. These forms will be completed and faxed to the IRB.

All protocol deviations occurring at each site that are not recorded on these forms will be listed in the Protocol Deviation Log, which will be routinely reviewed by the principal investigator.

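### ATP membership in Section 10.7 requires all protocol specifications to be met, can depend on events at or after a UTI, and feeds a primary-endpoint analysis with no cohort ranked as the main one

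*Combined protocol and SAP*

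**What the plan says.** All four cohorts are defined in Section 10.7 (Cohorts for Analyses).

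- **ATP:** "The according-to-protocol (ATP) cohort is the subset of Eval with subjects who meet all protocol specifications". The next sentence adds: "Those subjects who developed exclusion criteria while on study will be excluded from this cohort".
- **MITT** (randomized, at least one dose): "It will be used for analyses of primary and secondary endpoints, baseline characteristics, trial conduct, and significant protocol deviations".
- **Eval** (MITT with a follow-up visit and no antibiotic failure at Visit 1): "Subjects with any significant protocol deviations may be included in this cohort".
- **Use:** "Both Eval and ATP cohorts will be used to analyze the primary endpoints". Together with the MITT sentence, this puts three cohorts on the primary endpoints. None is called the main one.

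Section 10.7 gives no minimum number of applicators, no visit windows and no list of deviations that cost a woman her place in ATP. Section 8.6 separates significant deviations from others and names, among those that may be significant, "Deviations in the administration of study product". The ATP definition does not use that distinction.

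**The concern.** ATP membership is decided by what happens after randomization. That is normal for a per-protocol set, but three features make it a problem here.

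1. **No end point for judging compliance.** Women keep inserting applicators and attending visits after an on-study UTI (Sections 5.1, 6.3.5, 6.3.6, 6.8). A woman who has already had the outcome can therefore still leave ATP for something she does later.
2. **A direct link to the outcome.** Pyelonephritis is exclusion criterion 1 (Section 6.2.1.2.2). If her recurrence takes that form, the on-study exclusion-criteria sentence removes her because of an outcome-related event.
3. **Specifications that conflict.** Someone has to decide which ones count. Under Sections 6.2.2.1 and 9.1 the study statistician both holds the treatment assignments and analyzes the data. A list fixed in advance is therefore worth more than usual.

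At stake is an ATP estimate of unknown size, subject to outcome-dependent selection, standing beside MITT and Eval with nothing to say which prevails if they disagree.

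**Working it through.** **Step 1. Reproduce the planned power.** Section 10.4 gives 40% recurrence, a 50% reduction (so 20%), 250 women and power above 80%. Allocation is 1:1 (Section 6.2.2.1). Alpha is not stated; I assume 0.05 two-sided. With n per arm and a mean proportion of 0.30:

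power = Φ{ [0.20 − 1.96·√(2·0.30·0.70/n)] / √[(0.40·0.60 + 0.20·0.80)/n] }

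At n = 125 this is Φ{(0.20 − 0.1136)/0.0566} = Φ(1.527) = 93.7%. The stated figure reproduces.

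**Step 2. Find where ATP power drops below 80%.** The formula gives 80.4% at n = 82 and 79.9% at n = 81. The limit is about 164 women: 164/250 = 66%, or 164/276 = 59% with the enrolment figure in Sections 4.3 and 5.1.

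**Step 3. See what ATP size could be.** The documents give no adherence forecast, so these are assumed rates. If each unsupervised dose is taken as specified with probability q, independently, and the first of 15 is supervised, the share kept is q^14.

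| q | Share kept | Women of 250 | Power |
|---|---|---|---|
| 0.99 | 87% | 217 | 90% |
| 0.98 | 75% | 188 | 86% |
| 0.97 | 65% | 163 | 80% |
| 0.95 | 49% | 122 | 68% |
| 0.90 | 23% | 57 | 38% |

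**Step 4. Use the documents' own adherence clue.** Section 2.2.2.2 reports for LV-006 (five daily and two weekly doses) that 61% of 18 women on active product were colonized, which is 11. It adds: "Among LACTIN-V users with complete adherence to the study regimen, 78% were colonized at Day 10 or Day 28". With at most 18 women and at most 11 colonized, the only fraction rounding to 78% is 7/9. So 9 of 18 were fully adherent over 7 doses (inferred, not stated). The Wilson 95% interval is 29–71%. Carried to d doses under independence, the share kept is p^(d/7):

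- p = 0.50: 0.276 (d = 13) to 0.226 (d = 15), or 69 to 57 of 250 women; power 44% to 37%.
- p = 0.29, d = 15: 0.071, or 18 women; power 14%.
- p = 0.71, d = 13: 0.529, or 132 women; power 71%.

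**Step 5. Set the conflicting specifications side by side.** Section 4.2 totals 15 applicators and Section 5.1 dispenses a box of 15, while Section 6.7 requires 13 and says that number must not be exceeded. Section 4.3 puts visits at weeks 2, 4, 8, 12 and 16; Section 10.3 and the flow chart put them at weeks 3, 6, 10, 14 and 18. No woman can meet both members of either pair.

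**The case against.** A reader might infer that one missed applicator or one off-day visit removes a woman and that ATP will therefore be small. The documents do not support that.

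- **Missed doses.** Section 6.6 itself says of the daily phase: "if it is already within eight hours of her next dose, she should skip the missed applicator". It also allows a late weekly dose within four days, and Sections 6.3.4 and 6.4.2 allow deferral for menses. A woman who follows these is within protocol. Only misses outside them count.
- **Visits.** Visits 2–6 have no window and two schedules, so an off-day visit cannot be judged.
- **Section 8.6.** It says only that product deviations may be significant. Because Eval may keep significant deviators, ATP could be read as dropping only those. That is a fair reading, but the ATP sentence does not say it.
- **Size.** The 57–69 women in Step 4 rest on an inferred 9/18 and independent doses. Non-adherence clusters within women, so full adherence would probably fall more slowly. LV-003 used the same schedule of five daily doses and then ten weekly doses. The smallest denominators giving its ATP rates of 59.3% and 12.1% are 27 and 33, so at least 60 of 149 women (40%) were in ATP. That scales to about 100 of 250, with power near 59%. Its ATP definition is not shown, so this is only indicative.
- **After a UTI.** No passage says outright that compliance is scored after a UTI, and UTI treatment is not itself a breach. The point is that dosing continues and nothing stops the count.
- **Consequence.** MITT and Eval also address the primary endpoints, so nothing rests on ATP alone. Lower power in a per-protocol set is expected.

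These points limit the harm. They do not define who belongs in ATP, stop removal for an outcome-related event or rank the cohorts.

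**Conclusion.** The concern holds in a limited form. ATP as worded is strict, cannot be applied consistently because its specifications conflict, and can lose women because of events at or after the outcome. It is used for the primary endpoints with no statement that it is supportive.

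The firm number is the threshold: about 164 of 250 women for 80% power, assuming 40% versus 20% and a two-sided 0.05 test. Whether ATP falls below it is not known. At 98–99% adherence per dose it would not; the LV-006 carry-over gives roughly 18 to 132 women and 14–71% power, on 18 women and independent doses. The direction and size of any selection bias cannot be derived from the documents. This should be corrected, but it does not threaten the MITT analysis.

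**What to change.** In Section 10.7:

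1. Name MITT (or ITT) as the main cohort for the primary endpoints and label ATP supportive.
2. Replace the requirement to meet every specification with a closed list of important deviations, fixed before the treatment code is linked. Include a stated minimum share of scheduled applicators, counted only up to the first UTI or the end of dosing.
3. State that doses skipped, delayed or deferred as Sections 6.3.4, 6.4.2 and 6.6 allow do not exclude a woman.
4. State that no woman is removed for an outcome event, including a recurrence that is pyelonephritis.

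Elsewhere, reconcile the applicator counts (Sections 4.2, 5.1, 6.7) and the visit schedules (Sections 4.3, 5.1, 10.3 and the flow chart).

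The cost is wording, plus that reconciliation. The downside is that any adherence cut-off is a convention and the resulting ATP is less strict.
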